### 2.5 Masking

All outcome data will be analysed masked to the trial arm. The assessment of educational attainment will be masked as it is independently administered by UNEB staff, who have no knowledge of arm

allocation. The principal investigator (PI) and the trial statistician will remain masked until data collection and analysis of all primary and secondary outcomes are complete. Participants, school staff, implementers (WoMena Uganda), and the clinical officer will not be masked because it will be clear whether the intervention is being implemented.

### 2.6 Timing of outcome assessments and analysis

The primary and secondary outcomes were assessed in June-August 2023, approximately one year after randomisation and 2-3 months following the completion of intervention delivery from the implementing partner. Diary data for the secondary outcomes on school and class attendance was collected for approximately 12 weeks from April 2023. Final analyses for all outcomes will be performed after the SAP is finalized and the dataset is locked.

## 3 Trial population

### 3.1 Eligibility criteria

#### School-level inclusion criteria:

- Mixed-sex secondary schools with S1–S4 classes
- Day or mixed day/boarding schools.
- At least minimal WASH facilities (including an improved water source and sex-specific sanitation facilities that are functional, usable, and accessible to female students at the time of the rapid assessment eligibility survey)
- Estimated enrolment of 50–125 female S1 students in Wakiso and 40–125 female students in S1 in Kalungu, based on the 2019 report on the Master List of Education Institutions in Uganda [8].

#### School-level exclusion criteria:

- Schools that are currently participating in a menstrual health-related programme
- Boarding schools with no day students
- Single-sex schools
- Schools exclusively for students with disabilities
- Schools where more than approximately ~10% of students or parents of students do not understand Luganda or English.

#### Participant-level inclusion criteria:

- Female students in the class cohort of S2 in 2022 who were enrolled in a trial school at the time of the baseline and/or endline survey
- Male students in the class cohort of S2 in 2022 who were enrolled in a trial school at the time of the baseline survey.
- For the diary sub-study, female trial participants were eligible if they reported having started menstruation at the time of the baseline survey.

#### 3.2 School recruitment

Schools were randomly selected from those eligible and willing to participate. They were screened for eligibility in two stages. First, an initial desk review and screening was conducted using the 2019 Master List of Education Institutions for Kalungu and Wakiso districts [8]. Schools that provisionally met the criteria were then stratified into government versus private schools and randomly ordered. Second, a rapid assessment study including phone interviews with head teachers and school observations was undertaken to further determine eligibility according to the criteria outlined above. The rapid assessment was completed according to the randomly ordered list until 60 schools were found to be eligible and willing to participate as demonstrated by signing a memorandum of understanding. School-level consent was sought from the head teacher or director.

#### 3.3 Participant recruitment

A CONSORT flowchart (Figure A1-A2) will show recruitment and follow-up of schools and female and male participants.

#### Female participant recruitment at baseline

Prior to the baseline survey, schools were asked to provide lists of all students enrolled in S2. Lists were initially collected beginning in November 2021 and later updated once schools reopened following COVID-19-related closures in January 2022. For eligible female students aged below 18 years, informed consent was obtained from a parent or guardian following informational meetings held at the schools. Students who were 18 years or older could provide informed consent themselves. Informed consent/assent was sought from students immediately prior to the baseline survey. Consent/assent to receive a menstrual cup was sought separately from consent/assent for the main trial. The intervention activities started on June 27th 2022 in Kalungu District and on July 26th 2022 in Wakiso District. Students were included in the baseline population if they completed the baseline survey prior to these dates.

#### Recruitment of trial participants post-baseline

Female students who joined the S2-S3 cohort up to 31st March 2023 are eligible for the endline assessment. Updated enrolment lists from schools were sought in Term 1 2023 to identify new joiners. Parent/guardian consent and student assent for these new joiners was sought prior to the endline assessments. Any students who had parent/guardian consent at the time of randomisation but had not completed the assent and baseline survey were recruited alongside the new joiners. Socio-demographic data were collected at the time of assent (recruitment).

#### Male students

Fifteen male S2 students per school were randomly selected to be recruited into a closed cohort at baseline. The enrolment lists provided by the schools were used as the sampling frame. Students were replaced by the next student on the randomly ordered list if they were found to have left the school, had been absent for the previous 3 school weeks, did not consent, or were unable to be reached on 3 visits to the school. For schools where the total number of boys in S2 was less than 15, all boys were eligible for participation. A waiver was obtained for parent/guardian consent. Male participants were asked for written informed consent. All male participants with baseline data were included in the cohort, even if enrolled after intervention activities started in the District as it is a closed cohort.

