### 2.4 Randomisation

The 60 trial schools were allocated using 1:1 restricted randomisation. Within each district, the schools were additionally stratified by median UNEB baseline examination score (high/low). Covariate-constrained randomisation was then used to minimise imbalance with respect to key school-level factors (mean baseline examination score, mean past school examination scores, mean baseline SDQ score, government vs. private school, mean score on the Menstrual Practice Needs Scale, menstrual cup uptake, and the number of S2 female participants). Stratification factors (district and high/low baseline examination score) will be included as fixed-effects in all analyses.

A list of 1000 eligible allocations was randomly generated from all allocations meeting the specified balance criteria. One allocation was randomly selected at semi-public randomisation ceremonies held in each district in the presence of representatives from schools, the District Education Officer (DEO), and the Ministry of Education and Sports (MoES), and Ministry of Health (MoH).

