### 5.3 Analysis of count outcomes

For count outcomes (i.e., number of knowledge questions correct among female and male participants), the intervention effects will be presented as incident rate ratios (IRR) with 95%CI estimated using RE Poisson regression models with a random intercept for school to adjust for within-school clustering. The models will include the cluster-level mean baseline outcome measure and stratification variables. The LRT will be used to obtain p-values. If there is evidence of over-dispersion, the RE negative binomial model will be used. If there are issues of non-convergence, the GEE Poisson or negative binomial model will be used. The results will be presented as shown in Table A5.

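### Boys first surveyed after activities began still feed the school-mean baseline covariate, which can absorb part of the effect on the two male outcomes

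*SAP*

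**What the plan says.** Boys (section 3.3, Male students): "Fifteen male S2 students per school were randomly selected to be recruited into a closed cohort at baseline". The section then keeps every boy who has baseline data, "even if enrolled after intervention activities started in the District as it is a closed cohort".

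Girls (section 3.3, Female participant recruitment at baseline): the section gives start dates of 27 June 2022 in Kalungu and 26 July 2022 in Wakiso, and then states: "Students were included in the baseline population if they completed the baseline survey prior to these dates".

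Model (section 5.3): it opens "For count outcomes (i.e., number of knowledge questions correct among female and male participants" and specifies "The models will include the cluster-level mean baseline outcome measure and stratification variables". Table 2 classes both 1a and 1b as counts for both sexes. Table A5 lists both male measures, with a footnote saying that results are adjusted for the baseline outcome. No section removes late-surveyed boys from the school mean, and no sensitivity analysis in section 5.7 addresses them.

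**The concern.** Being a member of a closed cohort and having a valid pre-intervention measurement are separate matters. The closed-cohort reason explains why a late-enrolled boy is followed to endline. It does not make his first survey a baseline in the sense that covariate adjustment needs, namely a value the intervention cannot have influenced. The SAP respects that distinction for girls and not for boys.

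Knowledge, myths and attitudes are what puberty education and the drama skit aim to change. If some boys in intervention schools answered their first survey after such content reached them, their school's mean is raised by the intervention, while control schools' means are not. Adjusting for that mean subtracts part of the effect. With at most 15 boys selected per school, each late boy carries at least 1/15 (about 7%) of the school mean, so a few can shift it. At stake is an underestimate of the effect on the only two outcomes measured in boys.

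**Working it through.** **The plan's own figures.** The SAP states no power or effect size for the male outcomes. Its figures for girls reproduce: 30 schools per arm, harmonic mean 60, ICC 0.05 and a standardised difference of 0.2 give a design effect of 1 + 59 x 0.05 = 3.95 and an effective size of 1800/3.95 = 456 per arm. Power is 84.3% (noncentral t, 58 df, two-sided 0.05), against 84% stated. With harmonic mean 40 it is 80.1%, against 80% stated. The ICC of 0.05 is borrowed below for boys, as an assumption.

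**Formula.** Let T be the true endline effect, f the share of intervention-school boys surveyed late, d the share of T they already show, and b the slope of the school endline mean on the school baseline mean. Exposure raises the intervention-arm baseline by f x d x T. The adjusted estimate is then T - b x f x d x T, so the share lost is **f x b x d**. It is a loss only if the early and final effects have the same sign.

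**Slope.** With m = 15 boys per school, ICC r, between-school correlation c and within-boy correlation w:

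b = [r c + (1 - r) w/m] / [r + (1 - r)/m]

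For r = 0.05 the denominator is 0.05 + 0.95/15 = 0.1133.

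- c = 0.5, w = 0.3: b = 0.0440/0.1133 = 0.39
- c = 0.8, w = 0.5: b = 0.0717/0.1133 = 0.63
- c = 1.0, w = 0.6: b = 0.0880/0.1133 = 0.78

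With r = 0.10 the range is 0.43 to 0.85.

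**Share of the effect lost** (f and d are assumptions):

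| f | d | b | Loss |
|---|---|---|---|
| any | 0 | any | 0% |
| 0.2 | 0.1 | 0.5 | 1% |
| 0.1 | 0.5 | 0.39 to 0.78 | 1.9 to 3.9% |
| 0.2 | 0.5 | 0.39 to 0.78 | 3.9 to 7.8% |
| 0.2 | 1 | 0.39 to 0.78 | 7.8 to 15.5% |
| 0.5 | 1 | 0.39 to 0.78 | 19 to 39% |

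**Simulation.** 30 + 30 schools ("The 60 trial schools were allocated using 1:1 restricted randomisation"), 15 boys each, r = 0.05, c = 0.8, w = 0.5, true effect 0.25 SD, 3,000 runs per setting. A school-mean analysis of covariance served as a linear stand-in for the random-effects Poisson model.

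| f | d | Effect retained, as planned | Power, as planned | Effect retained, pre-start covariate | Power, pre-start covariate |
|---|---|---|---|---|---|
| 0 | 0 | 101% | 95% | 100% | 95% |
| 0.1 | 0.5 | 97% | 94% | 100% | 94% |
| 0.2 | 0.5 | 95% | 94% | 100% | 94% |
| 0.2 | 1 | 88% | 89% | 100% | 93% |
| 0.5 | 0.5 | 84% | 85% | 99% | 89% |
| 0.5 | 1 | 68% | 67% | 100% | 89% |

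With no effect at either time, the planned analysis rejects in 5.1% of runs.

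**The case against.** The strongest reply is that the SAP permits late-surveyed boys without showing that there were many, or that any of them had been exposed. Bias needs three things together: late boys in intervention schools, content that had already reached them, and scores that had already moved. The dates are for districts, not schools, and the first listed element is teacher training, which is not in itself content delivered to boys. Section 2.6 puts endline in June to August 2023, 2 to 3 months after delivery ended. Delivery therefore ran for most of a school year, and a boy surveyed soon after the start could carry little of the final effect. This stands: the loss may be small or nil.

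A reader might infer that the male estimates are in fact biased, or that about a third of the effect is lost. The SAP supports neither. A loss of that order needs, for example, half the boys late and all of them showing the full final effect at their first survey (0.5 x 0.63 x 1 = 32%).

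It may also be said that any error is conservative. That is so when early and final effects agree in sign, but an avoidable underestimate is still worth removing.

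The statement in section 5.1 that no substantial baseline imbalance was found does not settle the matter. It refers to the baseline population, a term that section 3.3 defines under female recruitment.

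**Conclusion.** The inconsistency is in the text: the SAP applies a pre-start cut-off to girls' baseline surveys, none to boys', and then uses the boys' values as a baseline covariate. The consequence is conditional. The adjustment can absorb part of the effect on male outcomes 1a and 1b. On the assumptions above, the loss runs from nil to a few percent when late boys are few or little changed, and to about 8 to 16% with one boy in five late and a full early effect. The number of late boys, the date each school began and the covariate slope are not in the SAP, so the actual size cannot be stated. All other outcomes, including both primaries, are measured in girls and are unaffected, and type I error is not inflated. This is a cheap improvement, not a threat to the trial's main conclusions.

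**What to change.** 1. Keep every boy in the endline analysis. In section 5.3, state that the male school-mean baseline is computed, in both arms, only from surveys completed before 27 June 2022 (Kalungu) or 26 July 2022 (Wakiso), the rule already used for girls.
2. If a school has no boy surveyed before the start, use one pre-specified rule applied without regard to arm: the mean of its randomisation stratum, from pre-start surveys only.
3. Show the number of later-surveyed boys by arm in Figure A2.
4. Add one sensitivity analysis to section 5.7, named in advance: either the male models without the baseline covariate, or the models excluding the late boys.

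The cost is a few sentences and a date filter on data already collected. The downside is a noisier covariate in schools with few early surveys. In the simulation, power with the filtered covariate was 93 to 94% at f = 0.2 and 89% at f = 0.5, against 95% with no late boys. If late boys were in truth unexposed, that small loss of precision is the price of the safeguard.

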#### 3.4 Participant follow-up

#### Female participants

The endline survey was administered to all recruited female participants present in a trial school at endline (June-August 2023). The study team sought to actively trace female participants no longer enrolled in a trial school at endline (section 4.1), to capture reasons why. We will describe the proportion no longer enrolled at endline by arm and explore factors associated with this. Reasons include dropout from school or transfer to a non-trial school.

Female participants will be categorised as having dropped out of school if we know they are not currently enrolled in any school (including non-trial schools). They will be categorised as "missing" for dropout status if we cannot determine if they are in school.

#### Male participants

The endline survey will be administered to all recruited male participants who are attending the same school at endline. Reasons for loss to follow up include dropout from school or transfer to a non-trial school.

#### Withdrawal

Participants may withdraw from participation in the individual-level elements of the intervention, from further data collection, or from all aspects of the study including the use of previously collected data. Data from participants who withdraw consent/assent will only be used as indicated on their withdrawal form. The number of withdrawals will be shown in the CONSORT flow chart (Figure 1).

#### 3.5 Analysis populations

Primary analysis population: The primary analysis will be conducted according to intention-to-treat (ITT) principles. Schools will be analysed according to the arm they were randomised to regardless of whether they received the intervention. Enrolled female participants with endline survey or UNEB data will form the primary analysis population. Students who switched schools between baseline and endline will be analysed according to the school they are attending at endline.

Female closed cohort: An additional analysis will be carried out within the closed cohort of female participants recruited at baseline who are enrolled at the same school at endline. This replaces a classic per-protocol analysis (which is problematic as there is no clearly-defined appropriate comparison group of those who would have received the intervention if offered, in the control arm). The closed cohort analysis assesses the intervention effect among those who had the chance to be exposed to the intervention for the whole study period in both arms.

Male closed cohort: Outcomes among male students will be assessed in the closed cohort of male participants recruited at baseline who are enrolled at the same school at endline.

### 4 Outcomes

#### 4.1 Data sources

Data are collected at two main timepoints, recruitment and endline. Primary and secondary outcome data are collected through:

- A self-completed survey conducted among female and male participants, with urine samples collected from female participants reporting urogenital symptoms in the survey.
- An educational assessment independently administered to female S3 students by the Uganda National Exam Board (UNEB) from July 24-26th 2023. Only scores from trial participants will be used in analyses.
- Daily diaries on menstruation and school/class attendance prospectively completed by a subsample of participants for approximately 12 weeks prior to the completion of the endline survey.

Following the endline survey, phone calls were made to parents of female students who had not participated in the endline UNEB examination nor the endline survey. Data were collected on whether the participant was attending a trial school, attending a non-trial school, or not attending school. The main reason for the latter was obtained. If there was no response to phone calls after 5 attempts, the parent was deemed not reachable.

Further details about data collection and management are given in the trial protocol [7].

### 4.2 Primary outcome definitions

Table 1 below shows the primary outcomes, their measures, variable types, sources of the data, and the analysis population.

Primary Outcome	Measure	Variable type	Data source	Eligibility
Educational attainment	Performance on English, Mathematics, and Biology (weighted equally) taught during the intervention year, using standard normal (z) scores estimated from the trial data. A combined score was generated as a row mean of the z-scores (for the 3 subjects).	Continuous	UNEB examination	All female participants
Mental health problems	Mean Total Difficulties Score from the Strengths and Difficulties questionnaire (SDQ-25) [9]	Continuous	Endline survey	All female participants

#### Table 1. Primary outcomes

#### 4.3 Secondary outcome definitions

Table 2 below shows the secondary outcomes, their measures, variable types and sources of the data. The definitions of some measures were amended to ensure comparable denominators and minimise the number of separate measures for each outcome. Details on these changes and the variables used to construct the derived measures are presented in Annex 2.

#### Table 2. Secondary outcomes

Secondary outcome	Measures	Variable type	Data source	Eligibility
1. Knowledge of puberty and menstruation; myths & attitudes towards menstruation	
 
1a) Number of knowledge items answered correctly (out of 9).
 
1b) Number of myths & attitudes items with positive responses (out of 3)
 
	Count	Endline survey	All female and male participants (stratified by gender)
2. Menstrual practices at last menstrual period (LMP)	
 
2a) Use of only adequate menstrual materials that are appropriately cleaned or disposed of at LMP
 
2b) Mean score on Menstrual Practice Needs Scale (MPNS)[10]
 
	Binary Continuous	Endline survey	Female participants who reported having menstruated in the past 6 months 
3. Pain management at LMP	Use of an effective pain management method (at least 1 effective method and none of the ineffective methods listed  )	Binary	Endline survey	Female participants who reported having menstruated in the past 6 months, and who report pain at LMP 
4. Self-efficacy of MH	Mean score on Self-efficacy in Addressing Menstrual Needs Scale (SAMNS)[11]	Continuous	Endline survey	Female participants who reported having menstruated in the past 6 months 
5. Quality of life 	CHU9D score, calculated as a weighted sum using adolescent Ugandan utility tariffs	Continuous	Endline survey	All female participants
6. Prevalence of urinary tract infection (UTI)	Symptomatic UTI, defined as at least one genital symptom plus leucocyte esterase and/or nitrates with a urine dipstick test	Binary	Endline survey and urine Multistix 8 dipstick result	Female participants who reported having menstruated in the past 6 months 
7. School and class absence during menses	
 
7a) Odds of missing a full school day on period-days relative to non-period days
 
7b) Odds of missing lesson on a school day on period-days relative to non-period days
 
	Binary (per day) Binary (per day)	Daily diary	Random subsample of ~1500 post- menarchal female Participants 

8. School and class attendance overall	
 
8a) Odds of missing a full school day
 
8b) Odds of missing lessons on a school day
 
	Binary (per day) Binary (per day)	Daily diary	Random subsample of ~1500 post- menarche female participants 
9. Self-confidence in Mathematics and science abilities	
 
9a) Mean score on the Students
 
Confidence in Mathematics
 
scale [12]
 
9b) Mean score on the Students
 
Confidence in Science scale [12]
 
	Continuous Continuous	Endline survey	All female participants

Defined as using a disposable pad or tampon that is always able to be immediately disposed; a reusable pad, cloth/towel, or homemade pad that is washed with water and soap and dry before use; or a menstrual cup that is boiled during or just before/after LMP; and no inadequate materials reported. Washing and drying of materials was not measured at baseline; this outcome will be adjusted for the baseline measure of use of adequate menstrual materials only.

The MPNS score will be calculated as the weighted average of i) the core items and school-specific items (given 75% weight) and ii) the relevant material-specific items (given 25% weight), since participants answer a different number of items depending on the materials reported.

Pain strategies listed: nothing, *stretching*, *painkillers*, *eating foods with lots of water*, drinking soda, *exercising*, *drinking lots of clean water*, taking antibiotics, *holding a warm water bottle on the stomach*, eating spicy foods, other (italics = considered effective). If the strategy mentioned in "Other" was also effective, this was included, and similarly for non-effective methods. Additional effective strategies mentioned as "Other" were sleep/rest or drinking warm/hot water (the latter was combined with drinking lots of clean water). Additional ineffective strategies included "herbs".

Period defined as days with reported menstrual flow plus one day prior. School days exclude exam days and days when the participants' school was reported as closed (holidays and weekends)

 We do not anticipate an intervention effect on the denominator, but if there is imbalance by arm we will adjust for confounders associated with arm and the outcome

 The CHU-9D data will be included in the economic evaluation paper, not the main trial outcome paper  The diary data will be weighted by the inverse of the sampling fraction for each school

